- Tests two behavioral interventions in combination with Varenicline in a population of daily smokers with current or lifetime major depressive disorder
- Eligible patients are randomized to receive inform consent forms offering \$0, \$200, or \$500 incentives for participation
- Patients are enrolled at The University of Pennsylvania and Northwestern University; randomization is stratified by site

b. MOVE IT Trial

- The Mobility and Outcomes for Validated Evidence Incentive Trial (MOVE IT) (NCT 03321279)
- Aims to examine the impact of a supportive social incentive-based gamification intervention in the three months post-hospital discharge among general medical and cancer patients using wearable technology
- Eligible patients are randomized to receive inform consent forms offering \$0, \$100, or \$300 incentives for participation
- Patients are enrolled at the Hospital of the University of Philadelphia by a team of clinical research coordinators; randomization is stratified by clinical research coordinator
- By necessity, clinical research coordinators administering the consent process in both parent trials are unmasked to the incentive information being messaged to prospective participants. The introduction to the study and the informed consent process have been robustly scripted for research staff involved in both trials to ensure that messaging is consistent and biases are minimized.

4. Population

Eligibility for RETAIN is contingent on eligibility for the BASC and MOVE IT parent trials.

- Adults age 18 years or older who are daily smokers with current or lifetime major depressive disorder without psychotic features (BASC)
- Adults age 18 years or older who are admitted for inpatient care to the Hospital of the University of Pennsylvania (HUP) on medicine or oncology floors (MOVE IT)

Patients randomized to RETAIN must be:

- Eligible for parent RCT
- 18 years or older
- English-speaking

In the BASC trial, prior knowledge of the incentive randomization or payment equalization used for this

study, which will be assessed with open-ended prompts during the first encounter, is an exclusion criterion. We will not assess for prior knowledge in the inpatient MOVE IT study population. However, only one patient per hospital room will be approached for the MOVE IT study to protect against contamination.

5. Primary outcome and analytic method

a. Primary outcome

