The primary outcome is the proportion of participants assigned to each incentive amount that consent to enroll in each of the two parent RCTs.

b. Primary analytic sample

Intention-to-treat (ITT) approach such that the analytic sample will include all patients randomized in the RETAIN trial, even if ultimately deemed ineligible for the parent trials.

c. Primary analysis

We will first assess bivariate relationships of incentives with the primary outcome using chi-square tests for comparisons of proportions. To examine the hypothesized statistical interactions, we will use logistic, linear, or quantile regression, as appropriate based on outcome parameterizations and distributions. In the above analyses we treated incentive as an ordered variable. In all analyses in which the parent trial enrolls in multiple centers, we will model the center from which patients are recruited as a fixed effect, thereby mitigating confounding by center and adjusting variance estimates for clustering of participants within centers. To adjust for chance covariate imbalance among arms, primary analyses will include covariates (see Table 1) in multivariable models if they are significantly associated with the intervention arm and predictive of enrollment in the parent trials in bivariate analyses. To avoid problems in estimating odds ratios due to sparse data, we will limit the number of covariates to no more than 1 per 10 participants enrolling in the parent trials. In all analyses related to the BASC parent trial, we will model the center from which patients are recruited as a fixed effect, thereby mitigating confounding by centers are recruited as a fixed effect, thereby mitigating confounding by center and adjust related to the BASC parent trial, we will model the center from which patients are recruited as a fixed effect, thereby mitigating confounding by center and adjusting variance estimates for clustering of participants within centers.

Our analyses to rule out undue and unjust inducements entail three primary covariates: risk perception, annual household income, and economic well-being. All models will use enrollment in the parent trial as the outcome. To determine if incentives represent undue inducements for research participation, we will test the statistical interaction between incentive size and the primary covariate of risk perception on

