Retention through the end of treatment sessions: To assess the impact of incentives on retention status in the protocol, we will disburse payment in two installments- one as soon as possible after debriefing and one during the patient's last week of treatment therapy or study intervention. The denominator for analyses of this outcome will be all those who received the first payment. We will assess if patients completed their treatments is associated to incentive amounts.

c. Analysis of secondary outcomes

We will first test the bivariate relationships between incentives and secondary outcomes using ANOVA or Jonckheere-Terpstra test for normally and non-normally distributed continuous variables, and chi-square tests (trend tests) for comparisons of proportions. In all of these analyses the incentive arm was included as an ordered variable. All the secondary outcomes are assessed among participants who consented for the trials. Due to limited sample size we plan to perform the unadjusted analyses.

Participants who consented and who didn't might be different meaning non response might not be random. To check if the inference is robust or not we plan to analyze the appropriate secondary outcomes 2 ways- unweighted and weighted. In survey weighted approach we plan to use propensity scores (inverse of probability of consent) as weights.

7. Sample size and statistical power calculations

a. Sample size

We plan to enroll 576 patients who are approached for participation in each parent trial, such that the total RETAIN sample will include 1,152 patients. However, RETAIN data associated with each of the two
parent trials will be analyzed separately in primary analyses.

b. Statistical power calculations

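### Final SAP 6.c analyses BASC secondary outcomes without site, against the promise in 5.c, and among consenters the site balance given by stratified randomisation is no longer guaranteed

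*Combined protocol and SAP*

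**What the plan says.** Final SAP 3.a on BASC: "Patients are enrolled at The University of Pennsylvania and Northwestern University; randomization is stratified by site".

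Final SAP 5.c, under the heading for the primary analysis: "In all analyses related to the BASC parent trial, we will model the center from which patients are recruited as a fixed effect". The same paragraph makes the same commitment in general terms for any parent trial with several centres. It opens the enrolment analysis thus: "We will first assess bivariate relationships of incentives with the primary outcome using chi-square tests for comparisons of proportions". It adds: "In the above analyses we treated incentive as an ordered variable". Multivariable models follow, with Table 1 covariates entered conditionally. Table 1 does not list site, and no main-effect model for enrolment is named.

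Final SAP 6.c on secondary outcomes names these tests: "ANOVA or Jonckheere-Terpstra test for normally and non-normally distributed continuous variables, and chi-square tests (trend tests) for comparisons of proportions". It restricts the population: "All the secondary outcomes are assessed among participants who consented for the trials". It then says: "Due to limited sample size we plan to perform the unadjusted analyses". As a robustness check it plans a second analysis weighted by the inverse probability of consent, without saying which variables enter the propensity model.

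**The concern.** None of the tests in 6.c, as named, carries a site term, and the section calls them unadjusted. An analyst cannot follow that and also fit centre in every BASC analysis.

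More than precision is at stake for these outcomes. Stratified randomisation balances site among everyone randomised. The secondary outcomes are measured in a subset selected after randomisation, by the very decision that the incentive is meant to change. If a larger incentive raises consent more at one site than at the other, that site makes up a larger share of consenters in the high-incentive arm. Any difference between sites in reading time, quiz score or perceived coercion would then be read partly as an effect of the incentive.

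**Working it through.** **The plan's own figure.** Final Protocol 6.a expects 50% of 576 to enrol: 576 × 0.50 = 288, as stated. If these were spread evenly, 288/3 = 96 per arm. Final SAP 5.c caps covariates at one per ten enrolling participants: 288/10 = 28.8, so 28. A two-site factor uses one.

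**Assumptions.** Site sizes, site consent rates, site-specific incentive effects and site differences in outcome are not in the documents. All are assumed below, with sites A and B of equal size.

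**Formulas** (high-incentive against zero-incentive arm, no true incentive effect on the outcome):
- Site A's share of consenters in an arm: s = pA/(pA + pB).
- Bias of the unadjusted contrast = d × (s_high − s_zero), where d is the site difference in within-site SDs.
- Consenters per arm: n = 96 × (pA + pB), from 192 randomised per arm and 96 per site.
- SE = √[(1 + d²·s_zero(1 − s_zero))/n_zero + (1 + d²·s_high(1 − s_high))/n_high].
- True two-sided level = Φ(−1.96 + bias/SE) + Φ(−1.96 − bias/SE).

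**One case in full.** Consent without incentive is 30% at A and 60% at B, and the incentive OR is 4 at A and 1 at B. At A the odds 0.4286 × 4 = 1.714 give p = 0.632. The share moves from 0.30/0.90 = 0.333 to 0.632/1.232 = 0.513. With d = 0.5, bias = 0.5 × 0.1795 = 0.090 SD and SE = 0.146. The ratio is 0.616 and the level about 9.5%.

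| Consent at zero, A / B | Incentive OR, A / B | Share of A, zero → high | d | Bias (SD) | Level |
|---|---|---|---|---|---|
| 40% / 40% | 2 / 2 | 0.500 → 0.500 | 0.5 | 0 | 5.0% |
| 30% / 60% | 2 / 2 | 0.333 → 0.381 | 0.5 | 0.024 | 5.3% |
| 30% / 60% | 3 / 3 | 0.333 → 0.407 | 0.5 | 0.037 | 5.8% |
| 40% / 40% | 3 / 1 | 0.500 → 0.625 | 0.5 | 0.063 | 6.9% |
| 30% / 60% | 4 / 1 | 0.333 → 0.513 | 0.5 | 0.090 | 9.5% |
| 30% / 60% | 4 / 1 | 0.333 → 0.513 | 0.8 | 0.144 | 15.7% |

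If incentive and site act multiplicatively on the consent probability, the share does not move at all (0.385 in both arms in the case tried).

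**Same calculation with effects in percentage points**, using 96 consenters per arm:
- A rises from 40% to 60% while B stays at 50%: share 0.444 → 0.545.
- A rises from 35% to 65% while B stays at 55%: share 0.389 → 0.542.
- With d = 0.5, SE = √(1 + 0.25 × 0.25) × √(2/96) = 0.149, and the levels are 6.3% and 8.1%.
- With d = 1, SE = √1.25 × √(2/96) = 0.161, and the levels are about 10% and 16%.

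**Simulation.** I ran 3,000 trials per scenario (576 patients, site-stratified 1:1:1, linear trend across arms). In the 30%/60%, OR 4/1 case the unadjusted level was 9.3% at d = 0.5 and 14.3% at d = 0.8. With site in the model, bias across all scenarios was −0.004 to 0.003 SD and the level 4.3% to 5.6%.

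**Enrolment.** All randomised patients are analysed (5.b) under site-stratified allocation, so omitting site gives no bias. The unadjusted test uses the total variance where only the within-site variance applies. With sites at 40% and 60%, within-site variance is 0.24 and total variance 0.25, a ratio of 0.96. The effective critical value is 1.96/√0.96 = 2.00, so a nominal 5% becomes about 4.5%. It becomes 4.0% with sites at 30% and 60%, and 3.2% at 30% and 70%.

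**The case against.** The strongest reply is that there may be no contradiction. Section 5.c is headed as the primary analysis, and *unadjusted* in 6.c may mean only without Table 1 covariates, among which site does not appear. The Original SAP's secondary section had a regression step with adjustments, and the sentence in 6.c appears to replace it. This reading is possible but does not settle the matter. If 5.c still applies, 6.c names no test that includes site. If it does not, the secondary outcomes have no site handling at all.

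It can also be said that 6.c recognises selection on consent and plans a weighted analysis. That could restore site balance, but only if site is in the propensity model, which is not stated. The weighted analysis is also a check; the log of SAP changes calls the unweighted analysis the primary approach.

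The figure of 288 is a planning value. Final Protocol 6.a says that sample sizes and consent rates may vary, and retention is assessed only in those who received the first payment. One site term remains cheap with considerably fewer participants.

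Four stronger readings are tempting, and the documents do not support them:
- A reader might infer that the enrolment comparison rests on a plain chi-square and is biased. The chi-square is a first step with incentive ordered, in a section that also promises centre, and it uses everyone randomised.
- A reader might take site imbalance among consenters as certain. Only the guarantee of balance is lost.
- A reader might carry away an error rate of 10-16%. That range needs an incentive effect confined to one site together with a large site difference in outcome.
- A reader might assume that consent was shown on a tablet at one site and a desktop at the other. Final Protocol 8.d.i mentions both devices for the two sites together and does not say that they differ by site. The SAP also says that consent was scripted for consistency.

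**Conclusion.** The concern stands for BASC secondary outcomes, at modest size. Sections 5.c and 6.c cannot both be followed as written, and the stated reason does not justify leaving out the randomisation stratifier. Bias is conditional: it requires that the incentive shifts the site mix of consenters and that site predicts the outcome. Under a common incentive odds ratio and a 0.5 SD site difference, the true level of a 5% test is 5% to about 6%. If the incentive works at one site only, it is about 6-10% at 0.5 SD, and it approaches 16% only at 0.8-1 SD. Every one of these figures rests on assumed site inputs.

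For enrolment the cost is slight conservatism, not bias. The gap there is that no site-adjusted main-effect test is named.

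**What to change.** For BASC in Final SAP 6.c, replace *unadjusted* with *adjusted for site only*, and name the tests:
- linear models with a site term in place of plain ANOVA;
- a site-stratified Jonckheere-Terpstra test for non-normal outcomes;
- a site-stratified (Cochran-Mantel-Haenszel) trend test for proportions.

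In 5.c, name the site-adjusted enrolment test for BASC: either the stratified trend test or a logistic model with site. In 6.c, list the propensity covariates and include site among them.

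The cost is SAP wording, stratified versions of tests already planned, and one degree of freedom; no new data are needed. The change removes only the site part of selection on consent. Other differences between consenters across arms remain, so the weighted analysis should be kept.

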the outcome of enrollment in the parent trials. We will test two interactions, each in a separate model to avoid collinearity, to determine if incentives represent unjust inducements: that between incentive size and the primary covariate of annual household income, and that between incentive size and the primary covariate of economic well-being. All analyses will be stratified by parent study.

Analyses of interaction terms will be structured as tests of non-inferiority. The null hypothesis, for both trials, will be that the use of incentives meets criteria for undue or unjust inducement. We can reject the null, and conclude the absence of undue or unjust inducement, if the interaction terms are "small" according to pre-specified criteria (in technical terms, the inferiority margin). Said a different way, our analyses are designed to determine if we can exclude the possibility that incentives represent undue or unjust inducements if the resulting interaction terms are sufficiently small. Specifically, we will use one-sided alpha levels of 0.05 to exclude, with 95% confidence, the possibility that any of these interaction odds ratios are >2.0.

We will explore temporal trends in incentives' effects over the study period using stratified analyses. If temporal trends are noted, as may occur if prospective patients learn of the incentives used in these studies, we will adjust for their influence by entering time as a covariate, modeled as a spline. We will evaluate potential effect modifiers (variables in Table 1) using stratified analyses. If differences among strata appear, we will formally test their corresponding interactions with the incentive amount.

TABLE 1 FACTORS FOR ADJUSTMENT AND EXPLORATION OF EFFECT MODIFICATION

Potential factors for adjustment			
Patient level covariates	Variable coding or definition		
• Age	Continuous		
• Gender	Binary		
• Race	Categorical		
Marital status	Categorical		
Education	Categorical		
Income	Categorical		
Economic well-being	Categorical		
Prior research participation	Categorical		
Attitudes towards research:	Continuous, measured using the Research Attitudes Questionnaire-7 (RAQ- 7).		

6. Secondary analysis

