The target enrollment of 576 patients in each RETAIN sub-trial was determined based on the primary goal of ruling out the possibility that incentives represent an undue inducement. Statistically, the presence of an undue inducement is represented by the interaction term between incentive amount and risk on the outcome of enrollment in the parent trial. Thus, we seek to rule out the possibility that the odds ratio associated with this interaction term is appreciably greater than a null value. To facilitate such a power estimation, we considered groups of participants with greater or less than the median level of risk perception who will be randomized to the highest incentive versus the lowest incentive. With an overall sample size of 576 participants in each parent study involved in the RETAIN trial, we assumed that 192 participants would be randomized to each of the 3 incentive arms. Assuming that randomization balances the incentives distribution within each risk-perception group, 96 participants will be assigned to each of the 3 incentives within both the high and low risk-perception groups. Among patients assigned to receive \$0, we set the OR contrasting the odds of enrollment between riskperception groups to 1, such that the OR for those assigned to receive the highest incentive (\$300 or \$500, in MOVE IT and BASC, respectively) represents the interaction odds ratio. We assume a true interaction OR of 1, and use a one-sided significance level of 0.0427 such that the upper 95.73% confidence limit on the observed OR falls entirely below the non-inferiority threshold. If the enrollment rate in the parent trials is 50%, we will have at least 80% power to rule out undue inducement, as represented by an interaction odds ratios of 2.0 or greater. However, because we will actually analyze risk as a continuous variable and incentive size as a 3-level variable, our true power will be greater than the estimates reported here. Similar analyses suggest similar levels of power to rule out the unjust inducement interaction terms.

8. Data Safety & Monitoring Board (DSMB)

We have chartered a DSMB to monitor RETAIN, with purview over both embedded trials, for the expressed purpose of evaluating evidence of undue or unjust inducement. Any serious adverse events, protocol deviations/violations, and unanticipated events will be reported to the IRBs with oversight of recruiting sites, the DSMB, and The National Cancer Institute.

9. Stopping Rules

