Trial stopping rules were approved by the Data Safety and Monitoring Board for the following events:

a. Undue inducement

To detect if incentives represent undue inducement that could distort voluntary informed consent, the research team will test the statistical interaction between incentive size and risk perception on the outcome of enrollment in the parent RCT.

b. Unjust inducement

To assess the presence of unjust inducement, or preferential participation among participants with either (a) lower income, or (b) reduced financial well-being, two interaction terms will be evaluated in separate models to avoid collinearity. Unjust inducement will be defined as a statistically significant interaction between (a) incentive size and annual household income, or (b) between incentive size and economic well-being, each on the outcome of trial enrollment. One or both of these interactions, if statistically significant in the direction that lower-income persons or persons with reduced economic well-being are more strongly motivated to participate by increasingly large payments, will be considered grounds for terminating the trial or suspending a trial arm.

10. Timing of analysis and adjustment of significance level

Interim analyses will be conducted after 50% and 75% of the data have accrued within each the BASC and MOVE IT trials. In contrast to the final analyses, which will be structured as tests of non-inferiority, the interim analyses will be conducted as superiority tests of the interactions, such that rejection of the null hypothesis indicates evidence of the presence of an interaction between incentive size and one of our three primary covariates. We will use 1-sided significance levels of 0.0055, and 0.0219.

11. Personnel

Interim analyses will be performed by the trial's primary statistician who will conduct all analyses blinded to trial arm. Investigators, the project manager, and the DSMB will remain blinded to treatment arm through completion of analyses. The data manager and faculty statistician have been unblinded as was necessary to perform essential functions of their roles.

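### The final non-inferiority test is decided at one-sided 0.05 in SAP 5.c but sized at 0.0427 in SAP 7.b; state one level and restate the power, which stays below 80% at either in the SAP's simplified calculation

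*Combined protocol and SAP*

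**What the plan says.** All references are to the Final Statistical Analysis Plan (part VI) unless stated.

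- **Section 5.c, Primary analysis.** The interaction tests are non-inferiority tests against an interaction odds ratio of 2.0: "we will use one-sided alpha levels of 0.05 to exclude, with 95% confidence".
- **Section 7.b, Statistical power calculations.** The trial is sized with a stricter bound on the same margin. The calculation will "use a one-sided significance level of 0.0427", so a 95.73% upper bound must lie below the threshold. The stated power is at least 80%, with 96 participants per cell, 50% enrolment and a true interaction odds ratio of 1.
- **Section 10**, headed "Timing of analysis and adjustment of significance level". On timing: "Interim analyses will be conducted after 50% and 75% of the data have accrued". On levels: "We will use 1-sided significance levels of 0.0055, and 0.0219". On the type of test: "the interim analyses will be conducted as superiority tests of the interactions", in contrast to the final analyses. It gives no level for the final analysis.

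No section names a spending function or says how 0.05 and 0.0427 relate.

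**The concern.** The deciding bound for the primary aim should appear once, or identically wherever it appears. Here a reader finds a 95% bound in one section and a 95.73% bound in another, both applied to the same final test and the same margin. A result that excludes 2.0 at 95% but not at 95.73% rules out inducement under section 5.c and fails to under section 7.b. There are three interactions in each of two sub-trials, so six tests are open to this.

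The stated power also belongs to a level that the analysis section does not use. If 0.0427 is meant as an adjustment for the interim looks, the plan should say so. It should also explain why looks that test a different hypothesis call for one.

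**Working it through.** **Inputs.** From 7.b: margin 2.0, true odds ratio 1, 96 per cell, 50% enrolment, level 0.0427. From 5.c: level 0.05. From 10: interim levels 0.0055 and 0.0219 at information fractions 0.50 and 0.75.

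**1. Where 0.0427 comes from.** O'Brien-Fleming-type (Lan-DeMets) spending of an overall one-sided 0.05 at fractions 0.50, 0.75 and 1.0 gives:

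| Look | Computed nominal level | SAP |
|---|---|---|
| 50% | 0.00557 | 0.0055 |
| 75% | 0.02190 | 0.0219 |
| Final | 0.04271 | 0.0427 |

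The three SAP levels together give an overall error of 0.04997 when the same test is repeated at each look. The classical O'Brien-Fleming boundary (0.0071, 0.0227, 0.0416) does not fit. The spending function is therefore inferred from the match, not read from the SAP.

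**2. Whether that adjustment is needed.** If one hypothesis were tested at all three looks with 0.05 at the last, the overall error would be 0.0562, and 0.0427 would be needed. Section 10 describes something else. An interim rejection signals that an interaction is present, and no interim look can lead to a non-inferiority claim.

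False non-inferiority is the probability, at a true odds ratio of 2.0, of passing both harm looks and then having the final upper bound below 2.0. By trivariate normal integration:

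| Final level | Harm looks test odds ratio 1 | Harm look stops if lower bound exceeds 2.0 |
|---|---|---|
| 0.05 | 0.0499 to 0.0500 | 0.0500 |
| 0.0427 | 0.0426 to 0.0427 | 0.0427 |

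The ranges cover both standard errors in step 3. The last column is included because section 11.c of the Final Protocol gives that stopping criterion.

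**3. The SAP's power figure.** Power = Φ(ln 2 / SE − z), with ln 2 = 0.693, z = 1.645 at 0.05 and z = 1.720 at 0.0427.

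- *Two-cell shortcut, as 7.b describes.* The odds ratio in the $0 arm is fixed at 1, so only the two high-incentive cells contribute. SE = √(2 / (96 × 0.25)) = 0.289.
- *Four-cell interaction.* The $0 arm is estimated too. SE = √(4 / (96 × 0.25)) = 0.408.

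The largest observed odds ratio that passes is exp(ln 2 − z × SE).

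| | SE | Power at 0.05 | Power at 0.0427 | Difference | Largest passing odds ratio at 0.05 / 0.0427 |
|---|---|---|---|---|---|
| Two-cell | 0.289 | 77.5% | 75.2% | 2.3 points | 1.24 / 1.22 |
| Four-cell | 0.408 | 52.1% | 49.1% | 3.0 points | 1.02 / 0.99 |

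The difference column is also the share of trials, at a true odds ratio of 1, in which the two rules disagree.

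The stated 80% is not reproduced. Other versions of the two-cell calculation (comparisons of proportions, unpooled variance, a margin on the risk difference) gave 72% to 75% at 0.0427 and 75% to 78% at 0.05.

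**The case against.** The best defence is that the two figures are compatible: 0.05 is the overall level and 0.0427 its final-look share. Step 1 supports this numerically, and the heading of section 10 announces an adjustment. So the numbers share a recognisable origin, and it would be too strong to call them irreconcilable. What the defence does not supply is the text. Section 5.c attaches 0.05 to a 95% exclusion, which is a decision bound rather than an overall budget, and the interim looks do not test the hypothesis that the budget would protect.

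Three further inferences are tempting, and the documents do not support them.

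- **That the type I error is inflated.** It is not, at either level (step 2). The sizing used the stricter level, so the mismatch is conservative.
- **That the threshold was left to be picked after the data were seen, or is a remnant of the 2020 SAP changes.** Section 5.c states a complete rule in advance, and 7.b is openly a simplified power estimate. The Original SAP already pairs both levels with superiority interim looks, and says that it was finalised before BASC or MOVE IT enrolment.
- **That the mismatch explains the gap from 80%.** The SAP claims 80% at 0.0427, and the shortcut gives 75.2% at that same level. Moving to 0.05 recovers 2.3 of the 4.8 missing points. The drop to about 50% comes from counting the sampling error of the $0 arm, which is a separate matter.

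The SAP also says that true power will be greater, because risk is analysed as continuous and incentive at three levels. That may be so, but it gives no figure to check.

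**Conclusion.** The point stands as an inconsistency in specification with small numerical consequences. The final test has two printed bounds, the section on timing and levels gives neither, and the design as written provides no error-control reason for the stricter one. The choice changes the conclusion in about 2 to 3% of trials at a true odds ratio of 1, and holds false non-inferiority at about 0.050 or 0.043. It is worth correcting because it concerns the deciding bound for the primary aim.

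The power statement needs restating in any case: on the calculation that section 7.b describes, it falls short of 80% at both levels.

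These results assume a normal approximation on the log odds scale, the SAP's own cells and 50% enrolment, no allowance for missing data (the SAP states none), and interim information proportional to the fractions given.

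**What to change.** 1. State one level and confidence bound for the final test, in the same words, in sections 5.c, 7.b and 10. One-sided 0.05 with a 95% upper bound is sufficient. If the sponsor prefers 0.0427, section 5.c should change to the 95.73% bound, and the reason and the spending function should be named.
2. Add a sentence to section 10 saying that the interim looks test for harm, cannot declare non-inferiority and spend none of its alpha.
3. Restate the power in section 7.b at the chosen level, saying whether the sampling error of the $0 arm is counted. If the planned model with continuous risk and three incentive levels is expected to do better, give the figure and its assumptions.

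The cost is a few lines of SAP text and one recalculated power figure. Aligning the levels needs no additional participants.
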